## PROTOCOL SYNOPSIS

TITLE	 Ga-RM2 PET/MRI for Detection of Regional Nodal and Distant Metastases in Patients with Intermediate and High-Risk Prostate Cancer
STUDY PHASE	Phase 2
INDICATION	Prostate cancer
INVESTIGATIONAL PRODUCT OR PROCEDURE	 Ga-RM2
PRIMARY OBJECTIVE(S)	To evaluate  Ga-RM2 PET/MRI for detection of regional nodal and distant metastases in patients with intermediate and high-risk prostate cancer scheduled to undergo prostatectomy with lymph node dissection.
SAMPLE SIZE	90 participants
GOALS	To allow the referring physicians in the GU Oncology group to provide their patients a specific molecular imaging test for prostate cancer that is currently used outside of the United States.  To refine the PET/MRI protocols in the setting of initial staging of patients with intermediate and high risk prostate cancers.

## SCHEMA

## LIST OF ABBREVIATIONS AND DEFINITION OF TERMS

Ga-68	Gallium-68
IRB	Institutional Review Board
IV	Intravenous
PET/MRI	Positron emission tomography – magnetic resonance imaging
SUV	Standardized Uptake Value
GRPr	Gastrin releasing peptide receptor
BPH	Benign prostate hypertrophy
PSA	Prostate specific antigen
PSMA	Prostate specific membrane antigen

## 1. OBJECTIVE

### 1.1 Specific Aim

To evaluate  $^{68}\text{Ga}$ -RM2 PET/MRI for detection of intermediate and high-risk prostate cancer prior to prostatectomy.

[figure not shown]

Figure 1. Chemical structure of  $^{68}\text{Ga}$ -RM2

## 2. BACKGROUND AND SIGNIFICANCE

Data from the American Cancer Society suggests that for 2015 in the United States prostate cancer will continue to be the leading non-cutaneous cancer diagnosis in males with 220,800 estimated new cases, and has the second highest mortality (after lung) with 27,540 estimated deaths (1). Initial screening and diagnosis relies on the digital rectal exam (DRE), prostate specific antigen (PSA), and transrectal ultrasound-guided core biopsies (2, 3). Subsequent treatment is multifaceted and may involve observation, surgery (prostatectomy), radiation therapy (external beam or brachytherapy), hormonal therapy, chemotherapy, or a combination of these (4-6).

The choice of treatment directly depends on the initial staging, as well as the patient's age, co-morbidities, and preferences. Prostate cancer staging is based on the tumor-node-metastases (TNM) classification. As outlined in the National Comprehensive Cancer Network guidelines, those patients requiring staging for additional therapy would need a bone scan and pelvic CT or MRI if the T-stage is greater than 2 or if the PSA or Gleason score is elevated ( $> 20 \text{ ng/mL}$  and  $> 8$ , respectively). The CT or MRI is primarily used to identify locoregional lymph nodes (thereby altering the N-stage), while the bone scan is primarily used to identify osseous metastatic disease (thereby altering the M-stage). In particular, the prognostic importance of bone metastases in patients with prostate cancer has been established. Patients with an abnormal bone scan at the time of diagnosis have a mortality rate twice as high as patients with normal bone scans (7).

However, at initial staging the issue is detection of pelvic and retroperitoneal small lymph node metastases that don't trigger size criteria on CT and MRI; bone metastases are a rare presentation.

Other tracers, such as  $^{18}\text{F}$ - or  $^{11}\text{C}$ -labeled choline and  $[^{11}\text{C}]$ -acetate, are used mainly for the diagnosis of recurrent (8-10) or metastatic (11) prostate cancer. Their feasibility in primary

diagnosis is limited because of uptake in benign tissue such as benign prostatic hyperplasia or inflammatory lymph nodes (12, 13).

Although choline based PET/CT is widely used outside the US for imaging prostate cancer, there have been numerous studies reporting a low sensitivity and specificity, especially at low prostate specific antigen (PSA) levels (14, 15). Consequently, improved imaging of prostate cancer is necessary. One novel promising method is PET imaging with F-FACBC, a new synthetic amino acid. Recent evaluations by Nanni et al. indicate that this tracer might be superior when compared to choline PET/CT (16). However, recent work indicates that F-FACBC uptake in prostate cancer is similar to that in BPH nodules (17). Prostate-specific membrane antigen (PSMA) continues to elicit high interest. This cell surface protein is significantly overexpressed in prostate cancer cells when compared to other PSMA-expressing tissues such as kidney, proximal small intestine or salivary glands. It therefore provides a promising target for prostate cancer-specific imaging. Recently methods have been developed to label PSMA ligands with Ga and F. Initial experience suggests that these novel tracers can detect prostate cancer relapses and metastases with high contrast by binding to the extracellular domain of PSMA, followed by internalization (18, 19). However, these promising agents do not detect all recurrences.

Consequently, improved imaging of prostate cancer continues to be an area of unmet clinical need. Ga-labeled DOTA-4-amino-1-carboxymethyl-piperidine-D-Phe-Gln-Trp-Ala-Val-Gly-His-Sta-Leu-NH2 (Ga-RM2, formerly also known as BAY86-7548 or Ga-DOTA-Bombesin) is a synthetic bombesin receptor antagonist, which targets gastrin-releasing peptide receptors (GRPr) (20). GRPr proteins are highly overexpressed in several human tumors, including prostate cancer (21). Because of their low expression in BPH and inflammatory prostatic tissues (22, 23), imaging of GRPr has potential advantages over current choline- and acetate-based radiotracers. Indeed, preclinical studies using BAY86-7548 have shown a high and persistent tracer uptake in mice bearing PC-3 tumor xenografts, which represent androgen-independent human prostate cancer with high GRPr expression (24).

## **Clinicaltrials.gov**

[figure not shown]
This study is registered on ClinicalTrials.gov as [NCT03113617](https://clinicaltrials.gov/ct2/show/NCT03113617).

In the first study with  $^{68}\text{Ga}$ -RM2 in patients with prostate cancer, 14 men scheduled for radical prostatectomy ( $n = 11$ ) or with biochemical recurrence after surgery or hormonal therapy ( $n = 3$ ) were enrolled. The patients received an intravenous injection of  $^{68}\text{Ga}$ -RM2 followed by over 60-minute dynamic imaging of prostate gland ( $n = 10$ ) and/or subsequent whole-body imaging ( $n = 14$ ). The visual assessment of PET/CT images included evaluation of intraprostatic

(12 subsextants) and pelvic nodal uptake of  $^{68}\text{Ga}$ -RM2 in 11 surgical patients and detection of potential metastatic foci in all patients. In patients with biochemical recurrence, results were compared with those of either  $^{11}\text{C}$ -acetate ( $n = 2$ ) or  $^{18}\text{F}$ -fluoromethylcholine ( $n = 1$ ) PET/CT. The authors reported a sensitivity, specificity, and accuracy of 88%, 81% and 83%, respectively, for detection of primary prostate cancer and sensitivity of 70% for metastatic lymph nodes using histology as gold standard (26). In our experience,  $^{68}\text{Ga}$ -RM2 compared favorably against  $^{68}\text{Ga}$ -PSMA (27).

## 2.2 Study Design

This is a prospective, single center, single-arm study enrolling 90 participants with intermediate and high-risk prostate cancer. Eligible participants will undergo baseline assessments at enrollment. Study participants will receive  $^{68}\text{Ga}$ -RM2 and undergo a PET/MRI scan. All patients will first be seen by a Stanford Cancer Institute physician and then referred if appropriate on clinical grounds to [name] or his colleagues for this study. The following steps will take place.

1. After signed the informed consent document, participants will be given a copy of the signed form
2. Participant will be asked to drink 1 to 2 glasses of water before arrival at the clinic
3. Participants will be weighed and vital signs (heart rate and blood pressure) will be recorded
4. Study personnel (eg, technologist) will verify subject identity; radiopharmaceutical identity; dose; and administration route. Participant will be injected IV with  $140 \text{ MBq} \pm 20\%$  of  $^{68}\text{Ga}$ -RM2
5. Participant will void immediately prior to the scan
6. Approximately 50 to 100 minutes after the radiopharmaceutical IV administration, data acquisition will begin in the pelvic region and move toward the head. First, localizer MRI scans will be performed to define the table positions. After correct positioning of the spatial acquisition windows is ensured, the combined PET/MRI acquisition will be initiated with 3 to 5 table positions at a 4-min acquisition time per table position.
7. Vital signs (heart rate and blood pressure) will be recorded again at the completion of the study.
8. Participants will be dismissed.
9. Participants will be contacted at 24 to 72 hours following the scan in order to capture potential late occurring Adverse Events.

The  $^{68}\text{Ga}$ -RM2 PET/MRI may be repeated at the completion of treatment to evaluate response to therapy, if requested by the treating physician.

### **3. PARTICIPANT SELECTION AND ENROLLMENT PROCEDURES**

#### **3.1 Inclusion Criteria**

- Older than 18 year-old
- Biopsy proven prostate adenocarcinoma
- Planned prostatectomy with lymph node dissection
- Intermediate to high-risk disease (as determined by elevated PSA [PSA>10], T-stage [T2b or greater], Gleason score [Gleason score > 6] or other risk factors)
- Able to provide written consent
- Karnofsky performance status of ≥50 (or ECOG/WHO equivalent)
- Diagnostic CT or MRI performed within 30 days prior to the Ga-RM2 PET

#### **3.2 Exclusion Criteria**

- Inability to lie still for the entire imaging time (approximately 30 minutes)
- Inability to complete the needed investigational and standard-of-care imaging examinations due to other reasons (severe claustrophobia, radiation phobia, etc.)
- Any additional medical condition, serious intercurrent illness, or other extenuating circumstance that, in the opinion of the Investigator, may significantly interfere with study compliance
- Metallic implants (contraindicated for MRI)

#### **3.3 Informed Consent Process**

All participants will be provided a consent form describing the study with sufficient information for participants to make an informed decision regarding their participation. Participants must sign the IRB approved informed consent prior to participation in any study specific procedure. The participant must receive a copy of the signed and dated consent document. The original signed copy of the consent document must be retained in the medical record or research file.

#### **3.4 Study Timeline**

##### **3.4.1 Primary Completion:**

The study will reach primary completion 36 months from the time the study opens to accrual.

##### **3.4.2 Study Completion:**

The study will reach study completion 48 months from the time the study opens to accrual.

### **4. IMAGING AGENT INFORMATION**

#### **4.1 Study Agent**

We will use Ga-RM2 as the PET radiopharmaceutical. The administered dosage is 140 MBq ± 20% i.v.

#### **4.2 Specify the source of the study agent**

Molecular Imaging Program at Stanford  
Satellite Radiochemistry Facility  
[name], [REDACTED]  
[name]

#### **4.3 Describe how the agent will be requested and provide mailing address and phone number.**

Ordered in Radiology Information System (RIS), address per above.

#### **4.4 Agent Accountability**

RIS is password protected and part of the electronic medical records.

### **5. IMAGING SPECIFICS**

#### **5.1 Modality or Modalities to be used**

PET/MRI

#### **5.2 Details of Imaging (i.e. dynamic, static, number of scans, etc.)**

We will use  $^{68}\text{Ga}$ -RM2 as the PET radiopharmaceutical. The administered dosage is 140 MBq  $\pm$  20% i.v.

A localizer MRI scan will be performed at 45 minutes after injection of 140 MBq  $\pm$  20% of  $^{68}\text{Ga}$ -RM2 to define the table positions. After correct positioning of the spatial acquisition windows is ensured, the combined PET/MRI acquisition will be initiated with 3 to 5 table positions at a 4-min acquisition time per table position. A volumetric T1 acquisition with fat-water separation and motion correction to enable free-breathing will be obtained at each table position and used for the generation of attenuation maps and for anatomic allocation of the PET results. Simultaneously with the start of the T1 MRI sequence, the PET acquisition will start at the same table position, thus ensuring optimal temporal and regional correspondence between MRI and PET data. The PET acquisition time will be 4 min per table position, taking delayed acquisition times and radioactive decay into account. As the T1 will take less than 4 minutes, a rapid diffusion weighted MRI will also be performed. After completion of the PET acquisition, the table will be moved to the next table position and the procedure will be repeated. Upon completion of the PET acquisition for all stations, volumetric post-contrast T1- and T2-weighted MR images may be obtained at multiple stations as needed.

The PET emission scan is corrected using segmented attenuation data of the MRI scan. The PET images are reconstructed with a standard iterative algorithm. All images are reformatted into axial, coronal, and sagittal views and viewed with the software provided by the manufacturer (AW, GE Medical Systems).

## 6. STUDY PROCEDURES

### 6.1 Criteria for Removal from Study

The Protocol Director may withdraw subjects from the study for one or more of the following reasons: failure to follow the instructions of the Protocol Director and/or study staff; determination that continuing the participation could be harmful to the subject; the study is cancelled or other administrative reasons.

### 6.2 Alternatives

The alternative is to not participate in the study.

## 7. STUDY CALENDAR

	Pre-Study	Week 1	24 - 72 Hours Post-Study	12 Months
Informed consent	X			
Demographics	X			
Medical history	X			
Follow-up Call to Participant			X	
 Ga-RM2 PET/MRI		X		
Data analysis				X

## 8. ADVERSE EVENT REPORTING

We do not anticipate hazardous situations for the subjects as a result of this protocol. However, procedures will be in place for verification of correct radiopharmaceutical dose and route of administration (i.e., each dose will be double checked for dosimetry and quality by a researcher and technologist). The study Principal Investigator (PI) or his designee will report unanticipated AEs related to the Stanford CCTO Safety Coordinator within 10 working days of becoming aware of the event (5 days if the event is life-threatening or resulted in death) using the Adverse Events Communication Form. If the principal investigator determines the unanticipated adverse device effect presents an unreasonable risk to subjects, the study will be terminated as soon as possible, but no later than 5 working days after the PI makes the determination and no later than 15 working days after first receiving notification of the effect.

## 9. REGULATORY CONSIDERATIONS

### 9.1 Institutional Review of Protocol

The protocol, the proposed informed consent and all forms of participant information related to the study (e.g. advertisements used to recruit participants) will be reviewed and approved by the Stanford IRB. Any changes made to the protocol will be submitted as a modification and will be approved by the IRB prior to implementation. The Protocol Director will disseminate the protocol amendment information to all participating investigators.

## **9.2 Data Management Plan**

The Stanford Cancer Institute Data and Safety Monitoring Committee (DSMC) will audit study related activities to determine whether the study has been conducted in accordance with the protocol, local standard operating procedures, FDA regulations, and Good Clinical Practice (GCP). This may include review of regulatory binders, case report forms, eligibility checklists, and source documents. In addition, the DSMC will regularly review serious adverse events and protocol deviations associated with the research to ensure the protection of human subjects. Results of DSMC audits will be communicated to the IRB and the appropriate regulatory authorities at the time of continuing review, or in an expedited fashion, as needed.

## **10. MEASUREMENTS**

### **10.1 Study Endpoints**

#### **10.1.1 Primary endpoint:**

- i. Sensitivity, specificity, positive and negative predictive value of  $^{68}\text{Ga}$ -RM2 PET for the detection of regional nodal metastases compared to pathology at radical prostatectomy on a per patient basis.

#### **10.1.2 Secondary endpoint:**

- i. Sensitivity, specificity, negative and positive predictive value for detection of regional nodal metastases in comparison to cross sectional imaging performed contemporaneously with the  $^{68}\text{Ga}$ -RM2 PET.

#### **10.1.3 Exploratory endpoint:**

- i. One year PSA progression free survival, comparing patients with and without pelvic nodal metastases.
- ii. Correlation between  $\text{SUV}_{\max}$  from  $^{68}\text{Ga}$ -RM2 PET and short axis diameter of nodal disease on cross sectional imaging correlate to presence of true pathology.
- iii. Incidence of osseous and distant metastatic lesions.

### **10.2 Image interpretation:**

#### **10.2.1 $^{68}\text{Ga}$ -RM2 PET/MRI:**

The PET/MRI scans will be interpreted by ABNM certified Nuclear Medicine physicians and ABR-certified radiologists. Consensus read will be obtained for each scan. Each lesion will be tabulated and a comparison of lesion detection by each scanner will be conducted.

Visual interpretation of PET data:

Regions of suspected disease will be graded on a two-point scale by each reader (0 = Negative or 1 = Positive). A region will be judged as positive if at least one lesion in this region is visually positive.

- i. Lymph nodes will be considered positive if the  $^{68}\text{Ga}$ -RM2 uptake is focal and greater than adjacent background. Pelvic lymph nodes will be sub-classified according to their localization as follows: R/L obturator, R/L external iliac, R/L internal iliac and other (total of 7 subgroups).
- ii. Visceral lesions will be considered positive if the  $^{68}\text{Ga}$ -RM2 uptake is focal and greater than physiologic background activity of the involvement organ or anatomic site.
- iii. Bone lesions will be considered positive if the  $^{68}\text{Ga}$ -RM2 uptake is focal and greater than physiologic bone marrow.

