### **10.4 Statistical analysis:**

- a. Sample size: 90 patients in total. The power analysis is based on the comparison of sensitivity between conventional imaging and  $^{68}\text{Ga}$ -RM2 PET.
  - i. 30% of intermediate to high-risk patients have nodal metastases at prostatectomy.

- ii. Conventional imaging has a 45% detection sensitivity for nodal metastases on a per patient basis (2).
  - iii.  $^{68}\text{Ga}$ -RM2 PET has a 60% detection sensitivity for nodal metastases on a per patient basis.
- b. Statistical analysis: The sensitivity, specificity, positive and negative predictive value of  $^{68}\text{Ga}$ -RM2 PET for the detection on a per patient basis will be determined using the below criteria:
  - i. True positive patient:
    - 1.  $^{68}\text{Ga}$ -RM2 PET positive for regional nodes; pathology at prostatectomy positive for regional nodes.
    - 2.  $^{68}\text{Ga}$ -RM2 PET positive for regional nodes, pathology negative for regional nodes, imaging after prostatectomy demonstrates node was not removed at surgery, and follow-up biopsy or imaging demonstrates presence of nodal disease.
      - a. Criteria for positive node on follow-up imaging: imaging within 3-12 months, the node decreases by more than 30% (for patients undergoing systemic treatment or focal therapy at this site) or increase by more than 20% in short axis diameter in the absence of treatment (with a minimum of 3 mm in change in size).
  - ii. True negative patient:
    - 1.  $^{68}\text{Ga}$ -RM2 PET negative for regional nodes; pathology at prostatectomy negative for regional nodes.
  - iii. False positive patient:
    - 1.  $^{68}\text{Ga}$ -RM2 PET positive for regional nodes, pathology at prostatectomy is negative, and imaging after prostatectomy demonstrates that node is no longer present.
  - iv. False negative patient:
    - 1.  $^{68}\text{Ga}$ -RM2 PET negative for regional nodes, but pathology at prostatectomy is positive.
  - v. Non-evaluable:
    - 1.  $^{68}\text{Ga}$ -RM2 PET positive for regional nodes, pathology negative for regional nodes, imaging after prostatectomy demonstrates node was not removed at surgery, and no definitive follow-up is available.
    - 2. Patients with extrapelvic nodal metastases will not be included in this analysis if patients do not undergo prostatectomy.

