## Appendix: Inclusion/Exclusion Criteria Checklist

Protocol Title:	68Ga-RM2 PET/MRI for Detection of Regional Nodal and Distant Metastases in Patients with Intermediate and High-Risk Prostate Cancer		
Protocol Number:	IRB-40373		
Principal Investigator:	[name]		

Inclusion Criteria – “Yes” must be checked to be eligible (From IRB approved protocol)	Yes	No	Supporting Documentation
1. Older than 18 year-old			
2. Biopsy proven prostate adenocarcinoma			
3. Planned prostatectomy with lymph node dissection			
4. Intermediate to high-risk disease (as determined by elevated PSA [PSA>10], T-stage [T2b or greater], Gleason score [Gleason score > 6] or other risk factors)			
5. Able to provide written consent			
6. Karnofsky performance status of ≥ 50 (or ECOG/WHO equivalent)			
7. Diagnostic CT or MRI performed within 90 days prior to 68Ga-RM2 PET			

Exclusion Criteria – “No” must be checked to be eligible (From IRB approved protocol)	Yes	No	Supporting Documentation
1. Inability to lie still for the entire imaging time (approximately 30 minutes)			
2. Inability to complete the needed investigational and standard-of-care imaging examinations due to other reasons (severe claustrophobia, radiation phobia, etc.)			
3. Any additional medical condition, serious intercurrent illness, or other extenuating circumstance that, in the opinion of the Investigator, may significantly interfere with study compliance			
4. Metallic implants (contraindicated for MRI)			

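### PET/MRI is read by consensus with nothing masking readers to the CT/MRI done before it, so the likely comparator can influence borderline PET calls, in either direction

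*Combined protocol and SAP*

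**What the plan says.** **Index read (section 10.2.1).** "The PET/MRI scans will be interpreted by ABNM certified Nuclear Medicine physicians and ABR-certified radiologists", and "Consensus read will be obtained for each scan". A lymph node counts as positive if its "uptake is focal and greater than adjacent background". Each reader grades regions as negative or positive. The same section adds: "Each lesion will be tabulated and a comparison of lesion detection by each scanner will be conducted". It does not say what other imaging, reports or clinical data the readers may see, or in what order scans are read. No other section supplied contains a masking provision.

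**Prior imaging.** Section 3.1 makes this an entry condition: "Diagnostic CT or MRI performed within 30 days prior to the" PET. The appendix checklist gives a different window, "Diagnostic CT or MRI performed within 90 days prior to 68Ga-RM2 PET". The two need reconciling, but under either one the scan exists when PET is read.

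**Comparator.** The secondary endpoint in section 10.1.2 gives the accuracy of PET "in comparison to cross sectional imaging performed contemporaneously with the" PET. Section 10.4 states: "The power analysis is based on the comparison of sensitivity between conventional imaging and" PET. The plan does not say who reads the comparator or by what rule.

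**Timing.** Section 10.3 has the urologist told about PET-positive nodes and distant lesions before surgery is done or decided on. Some PET read must therefore come before pathology. The plan does not say that this read is the endpoint read, or that it is locked.

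**The concern.** The comparison of sensitivity is paired: the same node-positive patients are called by both tests. It measures what PET adds only if each call is made without the other. Here the index call is a visual judgement, and the likely comparator is already on file. A reader who knows of an enlarged node on CT may call borderline uptake positive; a reader who knows that the CT was clean may dismiss faint uptake. Either way, part of the CT/MRI result enters the PET result, and the difference between the tests no longer belongs to the tracer alone.

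The comparison most exposed is the secondary endpoint, which is also the stated basis of the sample size. The primary endpoint compares PET with pathology, not with CT/MRI, but it uses the same PET calls and so is open to the same influence. Upgrading could also cost specificity. If the read is neither masked nor locked, analysis cannot undo this; only a masked re-read could.

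**Working it through.** **Inputs.** From section 10.4: 90 patients, 30% node-positive, sensitivity 45% for conventional imaging and 60% for PET. Assumptions that are not in the plan: how far the two tests overlap, and the share *f* of discordant patients whose PET call is changed by knowledge of the CT/MRI. The plan's 90 cannot be reproduced, because section 10.4 gives no alpha, power, test or discordance rate. Masking does not alter that number.

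**Step 1: weight of one call.** 90 × 0.30 = 27 node-positive patients. One changed call moves sensitivity by 1/27 = 3.7 points.

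**Step 2: patients who could be moved (independent tests).**
- CT-positive/PET-negative: 0.45 × 0.40 = 0.18; × 27 = 4.9 patients.
- PET-positive/CT-negative: 0.60 × 0.55 = 0.33; × 27 = 8.9 patients.

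**Step 3: apparent PET sensitivity.**
- Upgrade only: 0.60 + 0.18*f*
- Downgrade only: 0.60 − 0.33*f*
- Equal deference both ways: 0.60 + 0.18*f* − 0.33*f* = 0.60 − 0.15*f*

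| *f* | Upgrade only | Downgrade only | Both equally |
|---|---|---|---|
| 0.25 | 64.5% | 51.8% | 56.3% |
| 0.50 | 69.0% | 43.5% | 52.5% |

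The planned difference of 15 points thus becomes 19.5 or 24 points with upgrading only, and 11.3 or 7.5 points with equal deference.

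**Step 4: overlap between the tests.** Halfway between independence and full overlap, both tests are positive in (0.27 + 0.45)/2 = 0.36. The discordant shares become 0.45 − 0.36 = 0.09 and 0.60 − 0.36 = 0.24. Upgrading then gives 0.60 + 0.09*f*, that is 62.3% or 64.5%, half the shift in step 3. At full overlap no CT-positive patient is PET-negative, and upgrading has no effect. The equal-deference result does not depend on overlap, because the two discordant shares always differ by 0.15.

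**Step 5: no true advantage.** Let both tests have 45% sensitivity and be independent. Each discordant share is 0.45 × 0.55 = 0.2475. The plan names no comparative test; an exact two-sided 5% McNemar test with 27 patients is used for illustration. The chance that it favours PET is:

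| *f* | Upgrade only | Both equally |
|---|---|---|
| 0 | 1.3% | 1.3% |
| 0.25 | 3.7% | 1.1% |
| 0.50 | 10.6% | 0.8% |

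With upgrading only, *f* = 0.15/0.2475 = 0.61 would create the whole planned gap where none exists. With equal deference there is no net shift in sensitivity. With overlap halfway to full, the 10.6% falls to 3.0%.

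**The case against.** The strongest reply is that the plan is silent on masking; it does not tell readers to look at the CT/MRI. A consensus read is not in itself an unmasked read, and individual readers grade regions too. That is true. The point is that an unmasked read would comply with the plan, and a report of the trial could not show otherwise.

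A reader might infer that the influence runs only towards PET. The documents do not support that. At the planned figures more patients are open to downgrading (8.9) than to upgrading (4.9), so equal deference lowers PET sensitivity.

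The positivity rule also limits the mechanism. Node size is not a criterion, so an enlarged node without focal uptake is negative by the written rule, and only borderline uptake should be open to persuasion. This stands, and it makes large values of *f* implausible.

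The index scan carries its own MRI: section 5.2 lists T1 and diffusion-weighted imaging, with optional post-contrast T1 and T2. Readers masked to the earlier scan would still see nodal anatomy. This also stands. Masking removes the separate scan and its report, not all anatomical information.

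A reader might also infer that PET is scored with pathology known. Section 10.3 implies a read before surgery; what is missing is a statement that this read is the one analysed.

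**Conclusion.** The point holds as a weakness in the reading method. The plan leaves the PET call open to influence from the CT/MRI required before it, and so does not ensure independent reads in the comparison that underlies the sample size. Neither the direction nor the size of any bias can be known from the documents. On the assumed values of *f*, apparent PET sensitivity ranges from 43.5% (downgrading half) to 69% (upgrading half) around a true 60%. Even two or three changed calls (7.4 or 11.1 points) are material against a planned 15-point difference.

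These figures rest on the 27 expected node-positive patients, the sensitivities in section 10.4, independence where stated, and values of *f* that have no source in the plan. That the eligibility scan is the comparator is an inference from sections 3.1 and 10.1.2; it is likely but not written. The change should be made. It is cheap now and cannot be recovered at analysis without a masked re-read.

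**What to change.** **In section 10.2.1, state that:**
- the endpoint score is made from the PET/MRI dataset alone, by the same readers, without the eligibility CT/MRI, its report or pathology;
- the read before surgery that section 10.3 already implies is the endpoint read, and the consensus score is locked before surgery;
- prior imaging may be opened after locking for the clinical report, without changing the endpoint score;
- the index test is PET/MRI, or PET alone. The endpoints say PET, the scan read is PET/MRI, and its own MRI stays visible to the readers.

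**In section 10.1.2,** say whether the eligibility CT/MRI is the comparator. If so, score it from the clinical report issued before PET, by a rule fixed before analysis, so that PET cannot influence the CT/MRI call either. Reconcile the 30-day and 90-day windows.

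**Cost.** A reading instruction and a locked form, with no extra readers, scans or patients, and a few minutes per scan. The information available to the treating team is unchanged. The masked result may be slightly less favourable to PET than an unmasked one.
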